1.1. Synopsis

Protocol Title: A Phase 2 Study of Once-Weekly LY3437943 Compared with Placebo in Participants Who Have Obesity or Are Overweight with Weight-Related Comorbidities

Short Title: Effect of LY3437943 versus Placebo in Participants Who Have Obesity or Are Overweight

Rationale:

Obesity is a chronic disease and its increasing prevalence is a public health concern associated with rising incidence of type 2 diabetes (T2D), increased risk for premature death, and increased risk for some cancers (AMA 2013; Council on Science and Public Health 2013; Lauby-Secretan et al. 2016). There remains an unmet need in the pharmacologic treatment of obesity for drugs that are safe, efficacious, and well tolerated.

LY3437943 is a novel synthetic peptide, which shows potent agonist action at glucose-dependent insulinotropic polypeptide (GIP), glucagon-like peptide-1 (GLP-1), and glucagon (Gcg) receptors (GIPR, GLP-1R, and GcgR). It includes a linear peptide component of 39 amino acid residues conjugated to a C20 fatty acid moiety. In nonclinical pharmacology models, LY3437943 demonstrated greater weight loss in diet-induced obese (DIO) mice compared with an existing GLP-1 receptor agonist (GLP-1RA). The body weight reduction in DIO mice was primarily due to loss of fat mass and was associated with lowered total plasma cholesterol and reduced liver fat content. In addition, LY3437943 demonstrated a greater effect on glucose-dependent insulin secretion compared with an existing GLP-1RA, as demonstrated by intravenous glucose tolerance test in lean rats. Data from the Phase 1 program in patients with T2D demonstrated that LY3437943 has the potential to induce clinically meaningful weight loss (that is, 5%-10% or more) with a safety profile consistent with other GLP-1 and GIP/GLP-1RAs. Study J11-MC-GZBF (Study GZBF) will investigate the safety and efficacy of 48 weeks of treatment with LY3437943, administered subcutaneously once weekly (QW), in participants who have obesity ($\text{BMI} \geq 30 \text{ kg/m}^2$) or are overweight ($\text{BMI} \geq 27 \text{ kg/m}^2$ and $< 30 \text{ kg/m}^2$) with weight-related comorbidities but without T2D. The primary objective will be the effect on percent change in body weight at 24 weeks. These data will support dose selection for Phase 3 studies in participants who have obesity or are overweight with weight-related comorbidities.

Objectives and Endpoints

Objectives	Estimands/Endpoints
Primary	

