The primary estimand (a precise definition of the treatment effect to be estimated) of interest in comparing efficacy of LY3437943 doses with placebo is the “efficacy estimand” (Section 1.1). The primary efficacy assessment, guided by the “efficacy estimand” will be conducted using the EAS (Section 3). A restricted maximum likelihood-based, dose-pooling, MMRM analysis will be used to analyze continuous longitudinal variables. All the longitudinal observations at each scheduled postbaseline visit will be included in the analysis. This dose-pooling variant of MMRM replaced the fixed effect of treatment group with that of the preplanned time-varying treatment doses at each time point in an effort to derive a more efficient estimator when the same treatment regimen over time is shared across the treatment groups due to preplanned titration (Qu et al. 2021). For example, in LY 4.0 mg (2.0 mg) and LY 8.0 mg (2.0 mg) arms, the doses administered for the first 4 weeks are both 2.0 mg. Therefore, pooling all the patients in these 2 groups provides a more efficient estimation in the effect of 2.0 mg which is also anticipated to increase the estimation precision for the later administered doses. The model for the analysis of the primary efficacy endpoint of percent change from baseline in body weight will include the fixed effects of treatment doses planned in the titration scheme: placebo, LY 1.0 mg, LY 2.0 mg, LY 4.0 mg (2.0 mg), LY 4.0 mg (4.0 mg), LY 8.0 mg (2.0 mg), LY 8.0 mg (4.0 mg), and LY 12.0 mg (2.0 mg), stratification factors including gender (males, females) and baseline BMI stratum (less than 36, greater than or equal to 36), and continuous, fixed covariate of baseline value, all nested within visits. An unstructured covariance structure will be used to model the within-participant errors. Significance tests will be based on LS means and robust ‘Huber-

White" standard errors. If this analysis fails to converge, the following covariance structures will be tested in order:

- autoregressive, and compound symmetry. The first covariance structure that converges will be used.

Unless specified otherwise, safety assessments will be guided by an estimand comparing safety of LY3437943 doses with placebo irrespective of adherence to study drug. Thus, safety analyses will be conducted using the SS.

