4.5.2. Bayesian Analyses for Dose-Response

The longitudinal dose-response model as proposed by Qu et al. (2019) will be adapted here. This model also considers the preplanned dose changes that occur during the titration period. Let $\theta = (\theta_1, \theta_2, \dots, \theta_m)$ be the doses a participant has planned to take and $t_c = (t_{c1}, t_{c2}, \dots, t_{cm})$ be the corresponding times when the dose changes where t_{ci} indicates the time for dose to change from θ_i to θ_{i+1} . Therefore, the mean function of the parameter of interest at time t is modelled by:

$$f_{\theta, t_c}(t) = f(t; \theta_1) + \sum_{i=1}^{m-1} [f(t - t_{ci}; \theta_{i+1}) - f(t - t_{ci}; \theta_i)]I(t > t_{ci}),$$

where $I(X)$ is the indicator function that takes value 1 when the condition X holds. The $f(t; \theta)$ is defined such that

$$f(t; \theta) = \frac{\lambda(\theta)(1 - e^{-k(\theta)t})}{1 - e^{-k(\theta)d}},$$

where d is the maximum duration of the treatment period in weeks ($d = 24$ for primary analyses while $d = 36$ for final analysis), $\lambda(\theta)$ is the dose-response function for the maximum response at dose θ and $k(\theta)$ is dose θ 's rate parameter. This formulation of the mean function $f(t; \theta)$ was introduced by Fu and Manner (2010) to characterize the change from baseline over time in a continuous outcome that could be approximated with a pattern of exponential decay. It assumes a monotone time profile with the maximum effect reached at time d . The longitudinal data $Y_{\theta, t_c, jt}$ for participant j at time t with titration scheme (θ, t_c) will be fitted by adding the error terms to the mean function $f_{\theta, t_c}(t)$ where

$$Y_{\theta, t_c, jt} = f_{\theta, t_c}(t) + \frac{s_j(1 - e^{-k(\theta_1)t})}{1 - e^{-k(\theta_1)d}} + \epsilon_{jt},$$

$s_j \sim N(0, \sigma_s^2)$ and $\epsilon_{jt} \sim N(0, \sigma^2)$ are independent, denoting between-subject variation and within-subject variation respectively. Given s_j , $Y_{\theta, t_c, jt} \sim N(f_{\theta, t_c}(t) + \frac{s_j(1 - e^{-k(\theta_1)t})}{(1 - e^{-k(\theta_1)d})}, \sigma^2)$.

For characterizing the body weight change, we use a different formulation of $f_{\theta, t_c}(t)$ that showed better fitting in the analyses of historical trials and simulation studies while keeping all other elements unchanged. In the new formulation,

$$f_{\theta, t_c}(t) = f(t; \theta_1) + \sum_{i=1}^{m-1} h(t - t_{ci})[f(t; \theta_{i+1}) - f(t; \theta_i)]I(t > t_{ci}),$$

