Where $h(t - t_{ci}) = \frac{(1 - e^{-\tau(t - t_{ci})})}{1 - e^{-\tau d}}$. The parameter τ controls the rate of change in the body weight when dose changes. The dose-maximum response function $\lambda(\theta)$ is provided below:

The dose-maximum response function $\lambda(\theta)$ is provided below:

- body weight.

A power model is assumed where

$$\lambda(\theta) = a + b * \theta^\gamma$$

γ is a sigmoidicity parameter indicating shape or steepness of dose response.

Other dose-response models for $\lambda(\theta)$ may be explored if the aforementioned dose-response models do not fit the data well, eg, Simple Normal Dynamic Linear Modeling. Additionally, the different formulation of $f_{\theta, t_c}(t)$ may also be considered if the current specification does not provide an adequate fit to the data.

The estimation of those parameters will be carried out in a Bayesian framework assuming noninformative priors for the hyperparameters in the model as follows:

$$\begin{cases} k(\theta) \sim \text{Uniform}(0,1), \\ \alpha_0, \alpha_1, \alpha_2, a, b \sim N(0, 100^2), \\ 1/\sigma^2, 1/\sigma_s^2 \sim \text{Gamma}(0.01, 0.01), \\ \gamma \sim N(1, 5). \end{cases}$$

Posterior inference will be drawn for the dose-response at time t of clinical interest and the 95% credible intervals will also be plotted.

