Sample size selection is guided by the objective of establishing superiority of each LY3437943 dose to placebo relative to the percent change in body weight from baseline to Week 24. The evaluation of superiority to placebo will be conducted for each of the 4 LY3437943 doses at 2-sided significance level of 0.05 using 2-sample t-test. Assuming a SD of 10%, the LY3437943 group mean percent change in body weight at Week 24 from baseline compared to placebo is assumed to be -8%. The chosen sample size provides at least 97% power to establish superiority of LY3437943 1 mg, LY3437943 4 mg, LY3437943 8 mg, or LY3437943 12 mg compared to placebo. No adjustment for multiplicity will be performed.

In addition, this sample size provides approximately 83% power to show that at least 1 LY3437943 dose has superior effects of reducing waist circumference compared with placebo at Week 24. This assumes a reduction of 5.8 cm in waist circumference compared with placebo at Week 24 and a SD of 9.6 cm.

6. Novel Coronavirus Disease 2019 Impact

The following additional statistical analyses may be performed at the primary database lock and final database lock to assess the impact of COVID-19 pandemic for all randomized participants if the data warrants:

- listing of all randomized participants who discontinue study due to COVID-19 pandemic
- listing of all study disruptions related to COVID-19 pandemic
- listing of AEs or deaths related to COVID-19 pandemic, and
- listing of important protocol deviations due to COVID-19 pandemic.

In case there is a larger impact of COVID-19 on the study, due to a shut-down or any other reason, more details for additional analyses may be provided.

For the primary endpoints and key secondary endpoints, missing data due to COVID-19 will be handled as described in Section [4.3.3](#).

7. Supporting Documentation

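### The exploratory Bayesian body-weight dose-response model, as written, does not adjust for sex, BMI stratum or baseline weight, which may cost some precision in its dose contrasts

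*SAP*

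**What the plan says.** SAP 4.5.2 gives the participant-level model in full. The response at time t is the titration-dependent mean function, plus a participant effect `s_j` (normal, mean zero) multiplied by an exponential time profile, plus residual error. The random terms "are independent, denoting between-subject variation and within-subject variation respectively". For body weight only the mean function is replaced, with the dose-maximum response taken as a + b*dose^gamma; the rest of the model is kept. The section allows other forms for the dose function and the mean function if fit is poor, but says nothing about adding participant covariates.

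On fitting, it states: "The estimation of those parameters will be carried out in a Bayesian framework assuming noninformative priors". The prior list that follows includes `alpha_0`, `alpha_1` and `alpha_2`, each N(0, 100^2). None of them enters a printed equation.

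Elsewhere the SAP adjusts. Randomisation is stratified by sex and BMI at 36 (SAP 1.2). The primary MMRM (SAP 4.1) includes "stratification factors including gender (males, females) and baseline BMI stratum (less than 36, greater than or equal to 36") and the continuous baseline value. The hybrid-estimand ANHECOVA (SAP 4.3.3) has the same covariates plus their interactions with treatment. The logistic models for weight-loss thresholds (SAP 4.4, Table GZBF.4.4) use the strata and the baseline value. The SAP version history gives efficiency as the reason for adopting ANHECOVA.

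**The concern.** The SAP aims for precision through covariate adjustment in its main weight models and gives no reason for leaving the dose-response model out. In that model, whatever sex, BMI stratum and baseline weight explain is counted as unexplained variation between participants. The balance that stratification provides is then not credited in the posterior for the curve.

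Precision has some value here. SAP 4.1 says the trial is not powered for comparisons among LY3437943 doses and will not make them unless otherwise specified, so a model that borrows strength across doses is a natural place to learn how doses differ. The protocol synopsis says of the trial as a whole: "These data will support dose selection for Phase 3 studies". Protocol 4.2 and 4.3 tie dose-exposure-response work to the choice of later doses. SAP 4.5.2 itself states no dose-selection rule.

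**Working it through.** **1. Reproduce the plan's own figure.** Protocol 9.2 and SAP 5 specify testing "at 2-sided significance level of 0.05 using 2-sample t-test", with "Assuming a SD of 10"%, a difference from placebo that "is assumed to be -8"%, and 48 completers per group (300 x 2/10 = 60 randomised; 60 x 0.8 = 48). The standard error of a difference is 10 x sqrt(2/48) = 2.041. The standardised effect is 8/2.041 = 3.92, which gives power of 97.5% (normal) or 97.2% (noncentral t). This agrees with the statement "The chosen sample size provides at least 97% power". The figure is not in dispute; it only sets the scale. Its SD is an input to an unadjusted t-test, so it says nothing about how much the covariates explain.

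**2. Simple approximation.** Let R2 be the share of total variance in weight change explained by sex, BMI stratum and baseline weight. The documents give no value, so a range is assumed.

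- Half-width of a dose-placebo difference: 1.96 x 10 x sqrt(2/48) x sqrt(1 - R2).
- Absolute mean for one group of 48 out of 240 completers: the covariate mean still has to be estimated from all 240, so the variance factor is 1 - R2 + R2 x 48/240 = 1 - 0.8 x R2.

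| R2 (assumed) | Half-width, dose minus placebo (points) | Narrower | Absolute mean: narrower |
|---|---|---|---|
| 0 | 4.00 | 0% | 0% |
| 0.02 | 3.96 | 1.0% | 0.8% |
| 0.05 | 3.90 | 2.5% | 2.0% |
| 0.10 | 3.80 | 5.1% | 4.1% |
| 0.20 | 3.58 | 10.6% | about 8% |

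**3. Check on the SAP's own model.** The standard errors were recomputed from the linearised information matrix of the 4.5.2 body-weight model. From the documents: the weight visits to Week 24, the planned titrations, 24 or 48 completers per arm, and the stated priors. Assumed: total variance 100, a between-participant share of 0.7 or 0.9, two dose-response shapes (b = -4, gamma = 0.5; b = -2, gamma = 0.8), and a near-flat prior for tau, for which the SAP lists none. R2 of the total variance was removed from the between-participant part. Across three contrasts with placebo at Week 24 (12 mg, 8 mg started at 4 mg, 1 mg), the narrowing was:

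- R2 = 0.05: 2.0-2.7%
- R2 = 0.10: 4.2-5.5%
- R2 = 0.20: 8.6-11.4%

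For example, with share 0.7 and the first shape, the standard error for 12 mg against placebo falls from 1.728 to 1.537 at R2 = 0.20, or 11.0%.

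**4. If the share is of between-participant variance only.** Covariates fixed at baseline do not reduce the within-participant variance. With a between-participant share of 0.7 (assumed) and a single visit, explaining 5% or 20% of that part gives 1 - sqrt(1 - 0.7 x 0.05) = 1.8% and 1 - sqrt(1 - 0.7 x 0.20) = 7.3%. Repeated visits would move these part of the way back towards 2.5% and 10.6%.

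**The case against.** The strongest reply has four parts.

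- **The omission may only be apparent.** `alpha_0` to `alpha_2` have priors and could be undeclared regression coefficients. They may equally be leftovers. As no printed equation contains them, they do not supply the adjustment; this part stands only as a reason to have them defined.
- **The gain may be negligible.** Nothing in the documents shows that these factors predict weight change. If the modelled response is percent change, it is already scaled to baseline weight; 4.5.2 says only that body weight change is being characterised. This stands, and it is why the size must be conditional.
- **The remedy has assumptions of its own.** Placing covariates in the mean of `s_j` makes their effect common to all doses and ties its time course to the starting dose's rate, even after titration. The ANHECOVA deliberately allows treatment-by-covariate interactions. If covariate effects grow with drug response, the additive form recovers less. This limits how much precision is gained; it does not make the unadjusted model preferable.
- **The section is exploratory,** and parsimony in a nonlinear model is defensible. That is fair, but the SAP does not offer it as a reason.

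A reader might also infer that adjustment is universal elsewhere. It is not. Baseline weight is not a randomisation factor, the adherer-estimand analysis averages imputed outcomes (SAP 4.3.3), and the Kaplan-Meier weight plots are unadjusted. Nor is 4.5.2 the only titration-aware analysis, since the primary MMRM uses the planned time-varying doses.

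**Conclusion.** The point holds as a minor, optional improvement. As printed, the Bayesian body-weight model has no term for sex, BMI stratum or baseline weight, unlike the primary MMRM, the hybrid-estimand ANHECOVA and the weight-threshold logistic models. Credible intervals for dose contrasts are conservative to the extent that these factors are prognostic. If they explain 5-20% of total variance, an assumed range, intervals for dose-placebo contrasts would be roughly 2-11% narrower with adjustment, and those for the absolute curve about 2-8%. The gain is less if the share is of between-participant variance only, and near zero if the factors are not prognostic.

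Two stronger readings are not supported. One is that the dose-response curve is biased: under randomisation, omitting these factors does not by itself bias dose contrasts. The other is that 4.5.2 decides the Phase 3 dose: the link to dose selection comes from Protocol 4.2 and 4.3, which speak of dose-exposure-response analysis generally. The primary test and the stated power are unaffected.

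**What to change.** In SAP 4.5.2, let `s_j` be normal with mean x_j'beta and variance sigma_s^2. Here x_j holds sex, BMI stratum and baseline weight, each centred, and each element of beta has prior N(0, 100^2). Because the model is linear in `s_j`, centring keeps the dose function as a population average. State that this assumes a covariate effect common to all doses, acting along the `s_j` time profile. Define `alpha_0` to `alpha_2` as these coefficients, if that is what they are, or delete them. If the sponsor prefers the unadjusted model, one sentence of justification would do.

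The cost is three extra parameters in one exploratory model and a few lines of SAP text. The covariates are already collected, and neither the primary analysis nor the sample size changes.

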4.6. Safety Analyses

Unless specified otherwise, safety assessments will be guided by an estimand comparing safety of LY3437943 doses with placebo irrespective of adherence to study drug. Thus, safety analyses will be conducted using the safety analysis set.

4.6.1. Extent of Exposure

Listing of exposure to LY3437943 and placebo will be provided by treatment group using data from the SS. Summary of duration of follow-up (defined as time in days from date of randomization to the date of the last study visit) and/or duration on study treatment (defined as time in days from date of first dose of study treatment to date of last dose of study treatment plus 7 days) will be provided by treatment group using data from SS, in the following period:

- 48 weeks plus safety follow-up (Visit 801) for all randomized participants

For the summary of duration on study treatment, the frequency and percentage of participants falling into the following range will be summarized by planned treatment group as well:

- greater than 0
- 4 weeks or longer
- 8 weeks or longer
- 12 weeks or longer
- 16 weeks or longer
- 20 weeks or longer
- 24 weeks or longer
- 28 weeks or longer
- 32 weeks or longer
- 36 weeks or longer
- 40 weeks or longer
- 44 weeks or longer, and
- 48 weeks or longer.

In addition, the frequency and percentages of participants falling into the following study treatment exposure ranges may be summarized by planned treatment group:

- 0 weeks,
- longer than 0 weeks to less than 4 weeks
- 4 weeks or longer to less than 8 weeks
- 8 weeks or longer to less than 16 weeks
- 16 weeks or longer to less than 20 weeks
- 20 weeks or longer to less than 24 weeks
- 24 weeks or longer to less than 28 weeks
- 28 weeks or longer to less than 32 weeks
- 32 weeks or longer to less than 36 weeks
- 36 weeks or longer to less than 40 weeks
- 40 weeks or longer to less than 44 weeks, and
- 44 weeks or longer to less than 48 weeks.

No p-values will be reported in these summaries as they are intended to describe the study populations rather than test hypotheses about them.

4.6.2. Adverse Events

A TEAE is defined as an event that first occurred or worsened in severity after baseline. The MedDRA LLT will be used in the treatment-emergent derivation. The maximum severity for each LLT during the baseline period including ongoing medical history will be used as baseline severity. For events with a missing severity during the baseline period, it will be treated as “mild” in severity for determining treatment-emergence. Events with a missing severity during the postbaseline period will be treated as “severe” and treatment-emergence will be determined by comparing to baseline severity.

For events occurring on the day of first taking study medication, the CRF-collected information (eg, treatment emergent flag, start time of study treatment and event) will be used to determine whether the event was pre versus posttreatment if available. If the relevant information is not available, then the events will be counted as posttreatment.

The counts and percentages of participants with TEAEs will be summarized by treatment using MedDRA PT nested within SOC. Statistical comparisons will be applied at both the SOC and PT levels. Events will be ordered by decreasing frequency within SOC. The SOC will be in alphabetical order. For events that are sex-specific, the denominator and computation of the percentage will include only participants from the given sex.

An overview of the number and percentage of participants who experienced a TEAE, SAE, death, discontinued from study treatment or study due to an AE, relationship to study drug will be summarized by treatment.

The counts and percentages of patients with TEAEs by maximum severity will be summarized by treatment using MedDRA PT. For each participant and TEAE, the maximum severity for the MedDRA PT is the maximum postbaseline severity observed from all associated LLTs mapping to the MedDRA PT. The maximum severity will be determined based on the nonmissing

severities. If all severities are missing for the defined postbaseline period of interest, it will show as missing in the table.

4.6.3. Patient Narratives

Patient narratives will be provided for all participants who experience any of the following “notable” events:

- death
- SAE, or
- permanent discontinuation of study treatment due to AEs.

Patient narratives (patient level data and summary paragraph) will be provided for participants in the randomized population with at least 1 notable event.

4.6.4. Vital Signs

In the case that multiple records of an individual vital sign are collected at the same visit, they will be averaged prior to being used for data summaries and analyses.

Descriptive summaries by treatment and by nominal visit will be provided for baseline and postbaseline values as well as change from baseline values.

Treatment differences in mean change will be analyzed using the MMRM model as described in Section 4.1 with all available data in the safety analysis set.

Counts and percentages of participants with treatment-emergent abnormal sitting systolic blood pressure, sitting diastolic, and pulse will be presented by treatment for participants who have both baseline and at least 1 postbaseline result. A treatment-emergent high result is defined as a change from a value less than or equal to the high limit at baseline to a value greater than the high limit at any time that meets the specified change criteria during the postbaseline period. A treatment-emergent low result is defined as a change from a value greater than or equal to the low limit at baseline to a value less than the low limit at any time that meets the specified change criteria during the postbaseline period. To assess decreases, change from the minimum value during the baseline period to the minimum value during the postbaseline period will be used. To assess increases, changes from the maximum value during the baseline period to the maximum value during the postbaseline period will be used. Both planned and unplanned measurements will be included in the analysis. The criteria for identifying patients with treatment-emergent vital sign abnormalities are stated in [Table GZBF.4.6](#).

Table GZBF.4.6. Categorical Criteria for Abnormal Treatment-Emergent Blood Pressure and Pulse Measurements

Parameter	Low	High
Systolic BP (mm Hg) (Supine or sitting – forearm at heart level)	≤ 90 and decrease from baseline ≥ 20	≥ 129 and increase from baseline ≥ 20
Diastolic BP (mm Hg) (Supine or sitting – forearm at heart level)	≤ 50 and decrease from baseline ≥ 10	≥ 90 and increase from baseline ≥ 10
Pulse (bpm) (Supine or sitting)	< 50 and decrease from baseline ≥ 15	> 100 and increase from baseline ≥ 15

Abbreviations: BP = blood pressure; bpm = beats per minute

The treatment-emergent high systolic blood pressure will also include the criterion (≥ 140 and increase from baseline ≥ 20). The data summaries and analyses specified in this section will also apply to the measurements from ABPM where the same criteria applied to pulse rate will be applied to the heart rate.

In addition, following analyses will be conducted by treatment:

- counts and percentages of participants who had resting heart rate changes from baseline at 2 consecutive visits of more than 10 bpm and/or 20 bpm
- counts and percentages of participants who had at least 1 resting heart rate exceeding 100 bpm, and
- counts and percentages of participants who had at least 1 resting heart rate exceeding 100 bpm occurring at 2 consecutive study visits.

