16. Have obesity induced by other endocrinologic disorders (for example, Cushing's syndrome) or diagnosed monogenetic or syndromic forms of obesity (for example, Melanocortin 4 Receptor deficiency or Prader-Willi Syndrome)
 17. Have a history of significant active or unstable Major Depressive Disorder (MDD) or other severe psychiatric disorder (for example, schizophrenia, bipolar disorder, or other serious mood or anxiety disorder) within the last 2 years
- Note:*** Participants with MDD or generalized anxiety disorder whose disease state is considered stable for the past 2 years and expected to remain stable throughout the course of the study, in the opinion of the investigator, may be considered for inclusion if they are not on excluded medications

18. Have a lifetime history of suicide attempt
19. Have a Patient Health Questionnaire-9 (PHQ-9) score of 15 or more at Visit 1

20. On the C-SSRS at Visits 1, 3, or 4, prior to randomization:
- a “yes” answer to Question 4 (Active Suicidal Ideation with Some Intent to Act, Without Specific Plan) on the “Suicidal Ideation” portion of the C-SSRS
 - or**
 - a “yes” answer to Question 5 (Active Suicidal Ideation with Specific Plan and Intent) on the “Suicidal Ideation” portion of the C-SSRS
 - or**
 - a “yes” answer to any of the suicide-related behaviors (actual attempt, interrupted attempt, aborted attempt, preparatory act, or behavior) on the “Suicidal Behavior” portion of the C-SSRS
- and**
- the ideation or behavior occurred within the past month
21. Have uncontrolled hypertension (systolic BP above or equal to 160 mmHg and/or diastolic BP above or equal to 100 mmHg). If a participant is on anti-hypertensive therapies, doses must be stable for 30 days prior to screening. For participants with uncontrolled hypertension at the screening visit, antihypertensive medication may be started or adjusted. Blood pressure must meet the protocol criterion for hypertension control by Visit 3 with stable treatment for at least 30 days
22. Have an elevated resting pulse rate (>100 bpm) at baseline
23. Have any of the following cardiovascular conditions within 3 months prior to Screening:
- acute myocardial infarction
 - cerebrovascular accident (stroke)
 - unstable angina, or
 - hospitalization due to congestive heart failure (CHF)

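### The treatment-emergent high blood pressure table cannot count a rise from a diastolic baseline above 90 mmHg yet keeps those participants in its denominator, and its text, limits table and added systolic criterion disagree

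*SAP*

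**What the plan says.** SAP 4.6.4 plans counts and percentages of participants with treatment-emergent abnormal sitting blood pressure and pulse.

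- **Event, high side.** "A treatment-emergent high result is defined as a change from a value less than or equal to the high limit at baseline", to a later value above that limit that also meets the change criterion.
- **Baseline value.** "To assess increases, changes from the maximum value during the baseline period to the maximum value during the postbaseline period will be used".
- **Denominator.** The counts and percentages "will be presented by treatment for participants who have both baseline and at least 1 postbaseline result".
- **Limits in Table GZBF.4.6.** Systolic "≥ 129 and increase from baseline ≥ 20" mmHg; diastolic "≥ 90 and increase from baseline ≥ 10" mmHg. The table carries no condition on the baseline value.
- **Added systolic rule.** After the table: "The treatment-emergent high systolic blood pressure will also include the criterion" of at least 140 mmHg with a rise of at least 20. No baseline condition is stated for it.
- **Ambulatory monitoring.** The section applies the same summaries to ABPM measurements.

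On entry, Protocol 5.2, exclusion 21, defines uncontrolled hypertension as "systolic BP above or equal to 160 mmHg and/or diastolic BP above or equal to 100 mmHg". In whole mmHg, participants may therefore enter with up to 159/99. Control has to be reached by Visit 3.

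**The concern.** The event rule and the denominator describe different groups. The rule can only be met by someone who starts at or below the limit; the denominator includes people who start above it. Entry admits such people, and at BMI 27 to below 30 a screening systolic of 130 or a diastolic of 80 is itself one way to qualify (Protocol 5.1). Using the highest baseline value widens the group, because one high screening reading is enough to put a participant above the limit.

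Two things are at stake. Large rises in participants who already have raised pressure may not appear in the only planned categorical blood pressure display, and the percentages that do appear are lowered by people who could not have the event. Separately, programming from the text, from the table or from the added criterion gives different counts, so the output depends on which sentence the programmer follows.

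**Working it through.** The documents give no figure for this table, so there is nothing to reproduce. The check has three parts.

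**1. Which baselines can be counted?** Inputs are the limits and rises above and the entry ceiling of 159/99. For each whole-mmHg baseline (systolic 100 to 159, diastolic 60 to 99), ask whether any later value up to 260 would count.

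| Reading | Can be counted | Cannot be counted |
|---|---|---|
| Diastolic, text: baseline ≤90, later >90, rise ≥10 | 60–90 | 91–99 |
| Diastolic, Table GZBF.4.6 alone: later ≥90, rise ≥10 | 60–99 | none |
| Systolic A: baseline ≤129, later >129, rise ≥20 | 100–129 | 130–159 |
| Systolic B: A, plus the 140 criterion with its own baseline condition (≤140) | 100–140 | 141–159 |
| Systolic C: A, plus the 140 criterion standing alone | 100–159 | none |
| Systolic, Table GZBF.4.6 alone: later ≥129, rise ≥20 | 100–159 | none |

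Examples:

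- Diastolic 95 to 115: not counted under the text, counted under the table.
- Systolic 135 to 165: not counted under A, counted under B, C and the table.
- Systolic 145 to 175 or 150 to 190: not counted under A or B, counted under C and the table.

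For a baseline of 129 or less, any later value of at least 140 with a rise of at least 20 already meets the 129 rule. Within the text's definition, the added criterion therefore changes the count only for participants who start above 129, and that is exactly where its baseline condition is left unstated. If it inherited the 129 condition it would add nothing, and the result would be that of A.

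**2. Strict or non-strict limit?** The text requires a value above the limit; the table accepts the limit itself. Systolic 109 to 129 (rise 20) and diastolic 80 to 90 (rise 10) count under the table and not under the text.

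**3. Dilution.** Let r be the incidence among participants at or below the limit at baseline, and s the share above it. Those above contribute no events under the text, so

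reported % = r × (1 − s) + 0 × s = r × (1 − s).

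Planned size per dose level and for placebo is 300 × 2/10 = 60. Both r and s are assumptions; the documents give neither.

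| s | At risk, of 60 | Above limit | Reported if r = 10% | Reported if r = 20% |
|---|---|---|---|---|
| 10% | 54 | 6 | 9% | 18% |
| 20% | 48 | 12 | 8% | 16% |
| 30% | 42 | 18 | 7% | 14% |
| 40% | 36 | 24 | 6% | 12% |
| 60% | 24 | 36 | 4% | 8% |

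The value of s is specific to each parameter and limit. For diastolic pressure it is the share above 90. For systolic pressure it depends on the reading in part 1, and under C no baseline is uncountable, so the formula does not apply.

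**The case against.** The strongest reply concerns systolic pressure. A reader might infer that nobody starting above the limit can ever be counted, so that a systolic of 150 rising to 190 is lost. The documents do not establish that. The added criterion carries no stated baseline condition, matters within the text's definition only for baselines above 129, and read as a stand-alone rule counts that participant. Table GZBF.4.6 on its own also counts every eligible baseline, systolic and diastolic. This stands: for systolic pressure the defect is an unresolved ambiguity, not a proven gap. It does not rescue diastolic pressure under the text, for which no second criterion exists.

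A reader might also infer that these participants' rises go unseen altogether. They do not. The by-visit summaries and the MMRM of mean change on the safety analysis set include them, and the adverse event definition in SAP 4.6.2 covers worsening. A mean does not show individual outliers, though, which is what this table is for.

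Nor do the documents support reading this as a biased treatment comparison. Randomization balances s across arms in expectation (blood pressure is not a stratification factor, so only in expectation). With r of 20% against 5% and s = 40%, the table would show 12% against 3%: the ratio stays at 4, while the difference falls from 15 to 9 percentage points. The distortion is mainly in absolute incidence.

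Finally, a baseline condition is normal for a treatment-emergent count, and the Phase 1 finding reported in Protocol 2.2 is a fall in systolic pressure with a rise in heart rate. Both are fair, and both argue for modest weight. Neither explains why the denominator includes people who cannot have the event. Elsewhere the SAP takes baseline status into account: the PHQ-9 outcomes are restricted by baseline category, and pancreatic enzymes, liver tests and calcitonin are displayed by it.

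**Conclusion.** The point holds in this form. Under the text of SAP 4.6.4, a baseline diastolic of 91 to 99 cannot produce an event although entry allows it, and the participant remains in the denominator. For systolic 141 to 159 the same is true only if a baseline condition also governs the 140 criterion, which the SAP leaves open. Text, table and added criterion give different counts for identical data.

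The printed incidence falls by the factor (1 − s). Over assumed shares of 10% to 30%, an at-risk incidence of 10% would print as 9% to 7%. The real share is unknown from the documents. The check assumes whole-mmHg values and that the baseline condition is judged on the highest baseline value.

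The consequence is limited to one categorical safety table and its ABPM counterpart. The primary analysis and the mean-change analyses are untouched. It is worth correcting because the correction is cheap and the present wording cannot be programmed unambiguously.

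**What to change.** In SAP 4.6.4:

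1. Reconcile the definition in the text, Table GZBF.4.6 and the added systolic criterion. State whether the baseline condition applies to the 140 criterion and, if so, with which limit. Use one convention, strict or non-strict, throughout; the low limits for blood pressure have the same mismatch and can be settled in the same edit.
2. Present the table by baseline category. In one row, show new abnormalities over participants at or below the limit at baseline. In a separate row, show participants already above the limit at baseline who meet the stated limit and rise, over the number who started above it.
3. Apply the same denominators to the ABPM version, using the ABPM baseline.

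The thresholds themselves need not change. Splitting is preferable to simply deleting the baseline condition, which would merge new abnormality with worsening, and to correcting the denominator alone, which would still leave the worsening uncounted.

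The cost is a few sentences and one extra row per parameter. No new data are needed. The extra row will be thin: with 60 per group and an assumed 10% to 30% above the limit, it rests on 6 to 18 participants and should be read descriptively.
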